An alternative analgesic technique is **cryoneurolysis**, consisting of the application of exceptionally low temperatures to *reversibly* ablate peripheral nerves, resulting in temporary pain relief termed “*cryoanalgesia*”.⁴ The intense cold temperature at the probe tip produces Wallerian degeneration—a reversible breakdown of the nerve axon—subsequently inhibiting transmission of afferent and efferent signals. Because the nerve endoneurium, perineurium, and epineurium remain intact, the axon regenerates along the exoskeleton at a rate of approximately 1-2 mm/day. While cryoneurolysis of peripheral nerves through surgical incisions has been commonly used to treat pain since 1961, the development of cryo probes that may be inserted percutaneously promise a revolution in the use of this modality. The combination of newly-designed narrow-gauge probes (immediate right) and ultrasound now make percutaneous cryoanalgesia as simple as placing a peripheral nerve block: the probe tip is inserted adjacent to the target nerve under ultrasound guidance, and a series of 1-minute freezing cycles are administered followed by probe withdrawal.⁵ *The procedure is essentially the same as placing an ultrasound-guided peripheral nerve block; however, instead of injecting local anesthetic, a gas circulates through the probe, inducing cold at the tip and freezing the target nerve.* Nothing remains within the patient and there is no external equipment to prepare or manage. Importantly, cryoneurolysis and the cryo probes are already approved by the United States Food and Drug Administration for the treatment of acute and chronic pain, so no additional regulatory approval is required for the proposed clinical trial.

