Theoretical benefits of cryoneurolysis include an ultra-long duration of action without opioid involvement, no catheter management/removal, the lack of an infusion pump and anesthetic reservoir to carry, an extraordinarily-low risk of infection (approaching zero), and no risk of local anesthetic toxicity, catheter dislodgement or leakage. With a single 8-minute percutaneous cryoneurolysis procedure consisting of several freeze/defrost cycles, a truncation of sensory nerve conduction is induced for 6-8 weeks (motor neurons variable) with the complete restoration of nerve structure and function following remyelination. Cryoneurolysis offers the possibility of potent, side effect-free analgesia outlasting the surgical pain, and obviating the need for postoperative opioids.

Hypothesis 1b and 1c (persistent, post-surgical chronic pain): Following mastectomy and other painful surgical procedures, moderate to severe pain within the acute postoperative period is closely associated with subsequent persistent postsurgical pain lasting months⁶ or even years.^{7,8} Such chronic pain has an incidence of 30-73%,⁸⁻¹⁰ and is strongly correlated with depression and anxiety.¹¹ There is evidence that intense analgesia immediately following surgery may decrease the incidence and/or severity of chronic pain.^{12,13} Potent analgesia can be provided with intercostal nerve blocks in which local anesthetic is percutaneously injected adjacent to the peripheral nerves innervating the

breast.^{1,13} While single-injection nerve blocks have a duration of approximately 8 hours,¹⁴ they have been associated with a lower incidence of chronic pain 4-12 months after mastectomy.^{13,15,16} Extending the block to 60 hours can further decrease the incidence and severity of chronic pain.¹⁷

Furthermore, while the prevalence of post-mastectomy phantom breast pain—painful sensations perceived in the breast that is no longer present¹⁸—varies greatly, it has been reported as high as 44%.⁹ There is prospective clinical evidence that following upper and lower extremity amputation, continuous brachial plexus, sciatic, and femoral nerve blocks may decrease the incidence and/or severity of phantom limb pain.^{19,20} Using cryoneurolysis, a dense, multi-week peripheral nerve block may be provided, offering not only the possibility of the block outlasting the surgical pain, but enabling an opioid-free recovery and dramatically decreasing the risk of chronic pain.

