Randomization will be stratified by surgery type (e.g., mastectomy, upper limb amputation, and lower limb amputation). Computer-generated randomization lists will be used to create sealed, opaque randomization envelopes with the treatment group assignment enclosed in each envelope labeled with the randomization number.

The specific nerves targeted will depend on the surgical site: intercostal nerves (4 levels depending on the specific surgical approach) for mastectomy; femoral/sciatic for lower limb amputation, brachial plexus (or terminal nerves) for upper limb amputation; infrapatellar branch of the saphenous nerve for knee arthroplasty; suprascapular nerve for shoulder surgery; intercostal nerves for VATS procedures, and the lateral femoral cutaneous nerve for skin grafting of the lateral thigh. The cryoneurolysis sites will be cleansed with chlorhexidine gluconate and isopropyl alcohol. Using the optimal ultrasound transducer for the specific anatomic location and subject anatomy (linear vs curvilinear array), the target nerves will be identified in a transverse cross-sectional (short axis) view.

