Incidence; duration each episode									•	•	•	•
Average & worst wound pain									•	•	•	•
Incidence; duration each episode									•	•	•	•

Difficulty sleeping due to pain?	•	•	•	•	•	•	•				
Awakenings due to pain	•	•	•	•	•	•	•				
Nausea (0=none, 10=vomited)	•	•	•	•	•	•	•				

* In addition to the above, for knee and shoulder surgery joint range of motion will be measured at various time points between 1-12 months as part of standard postoperative care; and for VATS, FEV1 will be measured at various time points during hospitalization as part of standard postoperative care.

Statistical Analysis. The limb amputation, total knee and shoulder arthroplasty, rotator cuff repair, VATS, and skin grafting subjects will be included in pilot studies to help power future clinical trials, so we will enroll a convenience sample and not have a pre-determined primary endpoint or statistical plan. However, the end points of most interest will be average pain score on postoperative day 2 for shoulder arthroplasty and skin grafting subjects, range-of-motion at 6 weeks for the rotator cuff repairs, range-of-motion for knee arthroplasty, and FEV1 for the VATS procedures.

For the subjects having mastectomy, we will power this study for an acute pain end point which will provide conclusive results for that end point; but, the data will also be used to help power a subsequent large, multicenter clinical trial for a chronic pain-related end point (which will require far more subjects than we will enroll for the current study).

For the mastectomy subjects, sample size calculations are centered around the hypothesis that cryoneurolysis decreases the incidence and severity of post-mastectomy pain in the week following surgery. To this end, the primary outcome is the average NRS (as administered as part of the Brief Pain Inventory) queried on the afternoon of postoperative day 2. The difference in the distribution of NRS between groups will be assessed using the Mann-Whitney U test. We approximate power using the two-sample t-test. Assuming a standard deviation of 2.25 NRS points,² and minimum clinically meaningful difference of 2 NRS points, n=30 patients per group provide 86% power with two-sided $\alpha=5\%$.

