10. HUMAN SUBJECTS

A convenience sample of subjects undergoing limb amputation (n=60), mastectomy (n=60), knee arthroplasty (n=60), shoulder arthroplasty and rotator cuff repair (n=60), VATS (n=60), and skin grafting of the lateral thigh (n=60) will be enrolled, with an additional 20 permitted to replace drop-outs. This will total up to 380 subjects.

Inclusion criteria: Adult patients of at least 18 years of age, (1) scheduled for a primary, unilateral total knee or shoulder arthroplasty, primary unilateral rotator cuff repair, VATS procedure, skin grafting of the lateral thigh, unilateral or bilateral mastectomy, or limb amputation distal to the femoral/humeral head and including at least one metatarsal/metacarpal bone; (2) a single-injection or continuous peripheral nerve block or epidural infusion planned for perioperative analgesia; and, (3) accepting of a cryoneurolysis procedure.

Exclusion criteria: (1) chronic opioid use (daily use within the 2 weeks prior to surgery and duration of use > 4 weeks); (2) pregnancy; (3) incarceration; (4) inability to communicate with the investigators; (5) morbid obesity (body mass index > 40 kg/m²); and, (6) possessing any contraindication specific to cryoneurolysis such as a localized infection at the treatment site, cryoglobulinemia, cold urticaria and Reynaud's Syndrome.

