14. POTENTIAL RISKS

1. Infection. There is the potential risk of infection since subjects will have a probe inserted through the skin. Since there will be nothing left going through the skin or in the subject after the probe is withdrawn, the risk of infection is very small and there has never been a report of permanent injury due to infection following cryoneurolysis.
2. Bleeding. The probe does not have an open tip and is not particularly sharp, so there is a very low risk of having any type of bleeding as a result of treatment. However, if it was to happen, we would hold pressure until the bleeding stopped.
3. The skin where the nerve is frozen could lose or gain color if the nerve is particularly close to the surface. However, this has never been reported for deeper nerves and using the probe that will be used for this study.
4. Since a nerve will be frozen, there is the chance of nerve injury. However, in 5 decades of using cryoneurolysis on peripheral nerves, only a single case of "neuritis" (nerve irritation) has been reported in medical journals, and this resolved after a few months.
5. There is the risk of loss of confidentiality. The following procedures will be done to maintain confidentiality: written, paper forms will be kept in a locked medical office and the locked Investigational Pharmacy's files. Computerized records containing personal health information will be stored on password-protected and encrypted computers.

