15. RISK MANAGEMENT PROCEDURES AND ADEQUACY OF RESOURCES

During the treatment, subjects will be continuously monitored with pulse oximetry, noninvasive blood pressure cuffs, and EKG (standard for catheter placement). Subjects will receive an IV so that emergency medications could be given, if needed. As described above, probes will be placed under sterile conditions as is standard-of-care for any percutaneous cryoneurolysis.

Following treatment, the subjects will be contacted daily for the first 4 days, and then on days 7, 14, 21, 28 as well as months 3, 6, and 12. Subjects will have a physicians' pager and cellular phone numbers available to respond 24 hours/day and 7 days/week for at least the first week following treatment.

The risks to confidentiality are the release of names/ telephone numbers/ demographic data (e.g. weight, age, height), which will be minimized by the use of password-protected computers and case report forms that will be stored in locked offices.

Subjects will be given clear instructions to call an investigator with any questions or concerns regarding their study participation. If a patient experiences an injury that is directly caused by this study, only professional medical care that they receive at the medical center. No other compensation is offered. Any adverse events will be reported to the IRB using the standard adverse events

reporting and upon continuing review (depending on severity, as defined by the IRB).

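### Motor and sensory loss are expected effects of active freezing, but weakness, falls and numbness are not in the risk list, the assessments or a by-arm safety table, so they cannot be compared systematically

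*Combined protocol and SAP*

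**What the plan says.** Section 7 (Background and Significance) describes the freeze as breaking down the axon, "subsequently inhibiting transmission of afferent and efferent signals". It gives the duration as "a truncation of sensory nerve conduction is induced for 6-8 weeks (motor neurons variable"), followed by full recovery of the nerve.

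Section 9 (Research Design and Methods) lists the target nerves by surgery: "femoral/sciatic for lower limb amputation, brachial plexus (or terminal nerves) for upper limb amputation", and the suprascapular nerve for shoulder surgery. Section 10 (Human Subjects) admits "limb amputation distal to the femoral/humeral head and including at least one metatarsal/metacarpal bone", so some amputation subjects keep most of the limb.

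Section 14 (Potential Risks) has five items: infection, bleeding, skin colour change, nerve injury and loss of confidentiality. The nerve item reads "Since a nerve will be frozen, there is the chance of nerve injury" and cites a single neuritis case that resolved.

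The only tolerability row in the section 9 assessment table is "Nausea (0=none, 10=vomited"). A footnote to the table adds that "for knee and shoulder surgery joint range of motion will be measured at various time points between 1-12 months" as part of usual care, and that FEV1 is taken in VATS subjects. On adverse events, section 15 (Risk Management) says "Any adverse events will be reported to the IRB using the standard adverse events" route, depending on severity; section 18 repeats this. The statistical text in section 9 covers the primary endpoint, demographics and secondary endpoints.

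**The concern.** By the plan's own account, loss of motor and sensory conduction is how the active treatment works and is not a rare accident. It should therefore occur mainly in one arm. A listed risk of nerve injury does not describe it, and nothing in the schedule asks about it.

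The stated purpose of the pilot is to refine the protocol and supply data for later, definitive trials. Those trials would need rates of weakness, falls and numbness under active and sham treatment. If both arms are not asked at the time, the data cannot be recovered later. The favourable risk judgement in section 18 would also go untested on the effects that section 7 predicts.

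**Working it through.** **Step 1. Predicted effects against what is listed and measured.**

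| Effect implied by section 7 | Section 14 risk list | Section 9 assessments | Section 9 analysis |
|---|---|---|---|
| Weakness (efferent block, variable duration) | Not named | No item | None |
| Falls (possible consequence of lower-limb weakness; a reviewer's inference) | Not named | No item | None |
| Numbness (sensory block, 6-8 weeks) | Not named | No item | None |
| Nerve injury | Named, one neuritis case | No item | None |

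**Step 2. Could an existing measure stand in?**

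- The Brief Pain Inventory interference items are presented as the impact of pain. A weak limb without pain need not register.
- The phantom-sensation questions concern the lost part, not numbness in what remains.
- Range of motion covers knee and shoulder surgery only, and FEV1 covers VATS only. The amputation cohort has neither, and neither measures strength or sensation.
- Nausea is scored in both arms but is not a nerve effect.
- Adverse-event reports to the IRB may capture some cases. The plan gives no definition, prompted list or tabulation by arm.

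**Step 3. What the cohort could show if asked.** The plan states no harm rate, so there is no figure to reproduce. Inputs: 60 amputation subjects planned (section 10), which is a target and not a minimum. The allocation ratio is not stated for this cohort. I assume 1:1, giving 60 / 2 = 30 active.

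Exact upper limit with zero events in n subjects: 1 − 0.05^(1/n) one-sided 95%, and 1 − 0.025^(1/n) two-sided 95%.

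- n = 30: 1 − 0.05^(1/30) = 9.5%; 1 − 0.025^(1/30) = 11.6%.
- n = 20 (allocation 1:2, active to sham): 13.9%; 16.8%.
- n = 40 (allocation 2:1): 7.2%; 8.8%.

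Chance of at least one event among 30 active subjects, 1 − (1 − p)^30:

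- p = 2%: 0.45
- p = 5%: 0.79
- p = 10%: 0.96

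Fisher's exact test against 0/30 in the sham arm, two-sided p = 2 × C(30,x)/C(60,x):

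- 5/30: 2 × 142,506 / 5,461,512 = 0.052
- 6/30: 2 × 593,775 / 50,063,860 = 0.024

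So a formal comparison would reach significance only from 6/30 against none. The realistic yield is description: counts and limits by arm. Shoulder surgery (arthroplasty and rotator cuff repair) also has a combined target of 60, so the same figures apply there under the same assumption.

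**The case against.** The strongest reply is that harms are not left uncollected. Subjects are contacted daily for four days, on days 7, 14, 21 and 28, and at months 3, 6 and 12. Adverse events go to the IRB, masked staff make the assessments, and Fisher's test is specified for categorical secondary data. Reported events could be split by arm afterwards. This stands against a reading that some may be tempted to take, that no harm can be compared between arms: nausea can be, and reported events could be counted. It does not supply comparable ascertainment of weakness, falls or numbness, because the plan does not say that anyone is asked about them.

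Other stronger inferences also go beyond the text:

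- *That subjects are not told of these effects.* Consent pages are not in the review copy, so only section 14 can be judged. Case report forms are not available either.
- *That every amputation subject has a main limb trunk frozen.* For the upper limb the plan allows terminal nerves instead.
- *That weakness will distort the range-of-motion results.* The femoral/sciatic and brachial plexus targets belong to the amputation cohort, which has no range-of-motion endpoint. For the suprascapular nerve this is possible, but the documents give no weakness rate or motor duration from which to judge it.
- *That lasting numbness is expected.* Section 7 predicts full recovery. The issue is numbness during the block, and whether recovery occurs as stated.

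The reply also raises a real cost. Numbness is a sign of active treatment. Asking about it before the day-2 pain score could unmask subjects or assessors, and early answers would be clouded by the local-anaesthetic blocks given to both arms. That is right, and it determines the timing of the fix.

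**Conclusion.** The point holds in a limited form. Sections 7 and 9 make motor and sensory loss an expected effect in the active arm, in nerves serving limbs that subjects may still use. Section 14 names only generic nerve injury, and section 9 neither asks about these effects nor plans an adverse-event table by arm. Systematic between-arm comparison of these harms is therefore not possible under the plan as written.

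It is a should-fix point about safety information. It does not touch the mastectomy primary analysis, and the documents do not show that subjects are at undue risk. The size, an upper limit of 9.5% or 11.6% after 0/30, rests on full enrolment of 60, an assumed 1:1 allocation and complete questioning. With numbers this small the gain is descriptive, not a powered test.

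**What to change.** 1. Reconcile section 14 with section 7, so that the risk list and the background agree on which motor and sensory effects are expected and for how long.
2. Add three yes/no items, on limb weakness, falls and persisting numbness, to contacts already scheduled after the day-2 primary pain score, for example from day 7 onward. Masked staff should ask them in both arms, after the pain items in each call.
3. State in the statistical section that these items and all adverse events will be tabulated by arm and by surgical cohort, with counts and exact confidence limits, as description only.

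The cost is a protocol amendment, a few more questions per call and one added table. No new visit or procedure is needed. A small unmasking risk remains for outcomes after day 7; the timing and order of the questions limit it and keep it away from the primary endpoint.

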15. RISK MANAGEMENT PROCEDURES AND ADEQUACY OF RESOURCES

During the treatment, subjects will be continuously monitored with pulse oximetry, noninvasive blood pressure cuffs, and EKG (standard for catheter placement). Subjects will receive an IV so that emergency medications could be given, if needed. As described above, probes will be placed under sterile conditions as is standard-of-care for any percutaneous cryoneurolysis.

Following treatment, the subjects will be contacted daily for the first 4 days, and then on days 7, 14, 21, 28 as well as months 3, 6, and 12. Subjects will have a physicians' pager and cellular phone numbers available to respond 24 hours/day and 7 days/week for at least the first week following treatment.

The risks to confidentiality are the release of names/ telephone numbers/ demographic data (e.g. weight, age, height), which will be minimized by the use of password-protected computers and case report forms that will be stored in locked offices.

Subjects will be given clear instructions to call an investigator with any questions or concerns regarding their study participation. If a patient experiences an injury that is directly caused by this study, only professional medical care that they receive at the medical center. No other compensation is offered. Any adverse events will be reported to the IRB using the standard adverse events

reporting and upon continuing review (depending on severity, as defined by the IRB).

16. PRIVACY AND CONFIDENTIALITY CONSIDERATIONS INCLUDING DATA ACCESS AND MANAGEMENT

Disposition of data. The original, hard-copy signed informed consent forms and case report forms will be stored within an investigator's locked office; and they will remain with the Principal Investigator for at least 7 years. Data will be entered into an Excel spreadsheet kept on a password-protected and encrypted computer and retained by the Principal Investigator for at least 7 years.

17. POTENTIAL BENEFITS

For subjects randomized to receive a sham treatment: There will be no difference between being in this study and deciding against participation. Therefore, there is no potential for direct benefits from this sham "treatment".

For subjects randomized to receive active cryoneurolysis: It is our hope that patients have a decrease in their acute and chronic postoperative pain (which might permit a decreased opioid consumption and opioid-related nausea/vomiting).

Possible benefits to others: Future patients may benefit if it is determined that cryoneurolysis decreases postoperative pain. In addition, with the opioid epidemic, any decrease in opioid requirements would be a welcome development.

18. RISK/BENEFIT RATIO

Chronic phantom limb and residual limb pain cause significant disability for patients, and there is currently a dearth of reliable treatments for this debilitating pain. Since cryoneurolysis has a very low incidence of complications, and there have no previous cases of permanent negative sequelae reported in the literature, we believe the potential risks to be minimal compared to the potential benefits.

Subjects will be given clear verbal and written instructions to call [name] in the Department of Anesthesia at UCSD, with any questions or concerns regarding their study participation. If a patient experiences an injury that is directly caused by this study, they will receive professional medical care at the University of California, San Diego. No other compensation is offered. Any adverse events will be reported to the UCSD IRB using the standard adverse events reporting website and on continuing review (depending on severity, as defined by the IRB).

